- ② Secondary objectives: To explore the improvement of cardioembolic stroke, cardiovascular complex events, recurrent stroke and all-cause death risk, quality of life, and cardiac function in the "multidisciplinary assisted diagnosis and treatment mode" group and the "routine diagnosis and treatment model group". The conventional diagnosis and treatment mode can match the patients not adopted in the same period and "multidisciplinary assistance in diagnosis and treatment mode".

Design type: A non-intervention, prospective, observational, real-world study (at least 1.5 years). No fixed diagnosis and treatment plan is set up in advance, and only a multidisciplinary assisted diagnosis and treatment mode is established. All treatment options are completely made by the clinicians who follow the expert consensus of relevant textbooks and clinical guidelines, and they are formulated according to the patients' conditions.

Study subjects: Collect high-risk patients from the Second Affiliated Hospital of Nanchang University and various hospitals of Jiangxi Province from September 2022 to September 2023.

Selection criteria: ① met the high embolic risk (including intracardiac thrombosis, intracardiac tumor, aortic atherosclerosis, atrial fibrillation, and spontaneous development of ultrasound) in the risk stratification criteria of The Chinese Expert Consensus on Cardiac stroke Diagnosis (2020); ② meets the surgical indications for cardiac diseases related to the Chinese Expert Consensus on the Treatment of Cardioembolic Stroke (2022) (including left atrial fibrillation occlusion, left atrial fibrillation ligation, and radiofrequency ablation of atrial fibrillation recommended for high-risk stroke patients with atrial fibrillation; Transcatheter PFO occlusion is recommended for cryptogenic stroke patients with high-risk PFO; Valvular repair or replacement, etc.); ③ understood and voluntarily signed the informed consent form.

Exclusion criteria: ① with severe mental disorder and unable to express intention; ② with other abnormal signs, laboratory tests and clinical diseases, not suitable to attend investigator; ③ and unable to complete long-term follow-up.

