Project objectives and assessment indicators: (a) establish a multidisciplinary cooperative diagnosis and treatment mode of cardiovascular and brain joint treatment, and routinely carry out interdisciplinary diagnosis and treatment of cardiovascular and cerebrovascular diseases; (b) develop an optimized diagnosis and treatment process, reduce treatment links, and save medical resources and costs.

Diagnosis and Treatment process (Figure 1):

Primary prevention (mainly for patients with high embolic risk, including valvular heart disease/intracardial tumor, thrombosis/atrial fibrillation/infective endocarditis/PFO, with or without a history of stroke):

- a) Patients with high risk of embolism, such as valvular heart disease/intracardiac tumors, thrombosis/atrial fibrillation/infective endocarditis/PFO, and patients with or without a history of stroke, were screened for stroke risk assessment in primary hospitals.
- b) Imaging diagnosis and treatment, such as cardiac color ultrasound, cardiac CTA, foaming test (right cardiography), transesophageal ultrasound, right atrial angiography, etc., should be developed according to the research needs, and the specialized diagnosis and treatment process at the recommended level should be formulated
- c) Health education and follow-up

Secondary prevention (emergency department mainly for patients with new stroke) :

- a) Primary doctors should do a good job in pre-hospital treatment of suspected stroke patients and transfer the patients to superior hospitals as soon as possible, so as to quickly identify the nature of stroke; Once it is clear that it is ischemic stroke, emergency treatment should be carried out according to the diagnosis and treatment process of ischemic stroke.
- b) When patients with sudden neurological deficits enter the emergency room, the stroke identification procedure and the treatment process of the stroke center should be initiated immediately, mainly using the BEFAST test /FAST test/" stroke 1-2-0 "method;
- c) After the disease stabilized, the examination related to etiological diagnosis should be improved (screening for valvular heart disease/intracardiac tumor, thrombosis/atrial fibrillation/infective endocarditis/PFO);
- d) Health education norms and follow-up

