3. Serious adverse events: Major adverse events may be drug-related, including but not limited to the following:
 - (a) Abnormal laboratory indicators (including liver and kidney function, etc.);
 - (b) Allergic reaction to antiplatelet drugs / anticoagulants;
 - (c) Stroke / transient ischemic attack or neurological deficit;
 - (d) Spontaneous bleeding: such as petechia, ecchymosis, digestive system and urinary system bleeding;
 - (e) Central nervous system damage.
4. Assessment of the severity level
Light: do not affect the daily activities;
In: affect daily activities;
Heavy: loss of daily activity ability.

7. Data collection and management

1. Survey content (CRF table)

variable:

- a) Basic information of patients: name, gender, age, education level, combined diseases, past medical history, etc.;
- b) Admission status: chief complaints of symptoms, general condition, vital signs, CHA2DS2-VASc score, nutrition questionnaire and epidemiological data etc.;
- c) Pre-treatment laboratory and instrument examination: biochemical indicators, nutrient index (one carbon unit substance), electrocardiogram, dynamic electrocardiogram, cardiac color doppler ultrasound, foaming test, cardiac CTA, craniocerebral CT and MRI, internal and external intracranial artery evaluation, etc.;
- d) Treatment medication; surgical conditions
- e) The occurrence of adverse events during the hospitalization period;
- f) Situation at follow-up: chief complaint of symptoms, general condition, vital signs, Quality of Life, HAS-BLED score, etc.;
- g) Laboratory and instrumental examination at follow-up: biochemical indicators, electrocardiogram, cardiac color ultrasound, cardiac CTA, craniocerebral CT and MRI, internal and external intracranial artery evaluation, etc.;
- h) occurrence of adverse events during follow-up.

2. Data management and statistical analysis

For All the subjects who have signed the informed consent form and are qualified to be selected, all the items in the electronic medical record report form should be carefully recorded in detail, without no empty or missing items.

The investigator records the data into the electronic medical record report according to the original records and inpatient records, and the investigator ensures that the data is true and accurate.

Data that are significantly high or outside the clinical acceptance range should be verified with necessary explanation by the investigator.

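### Quality of life is to be compared between self-selected groups, but the case report form list names it only at follow-up, so as listed there is no entry score to match on or adjust for

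*Protocol*

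**What the plan says.** The secondary objectives (Protocol, section 2), which concern both the multidisciplinary and the routine group, read: "To explore the improvement of cardioembolic stroke, cardiovascular complex events, recurrent stroke and all-cause death risk, quality of life, and cardiac function". The controls are described in the same place: "The conventional diagnosis and treatment mode can match the patients not adopted in the same period". Section 5.3 adds that, if a comparison with conventional care is made, the controls are contemporaneous patients matched on several factors, which it does not name.

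The group definitions in section 2 let the patient decide. Those who accept the multidisciplinary mode form one group, and those who do not are placed in the routine group.

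Section 7.1 lists the content of the case report form. Three items are recorded at entry.
- Item a covers patient characteristics and ends open-ended. It names sex, age, schooling, comorbidity and earlier illnesses.
- Item b covers the patient's state on arrival and reads: "Admission status: chief complaints of symptoms, general condition, vital signs, CHA2DS2-VASc score, nutrition questionnaire and epidemiological data etc".
- Item c covers the tests done before treatment; its opening part reads: "Pre-treatment laboratory and instrument examination: biochemical indicators, nutrient index (one carbon unit substance), electrocardiogram, dynamic electrocardiogram, cardiac color doppler ultrasound".

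Two items bear on this point at follow-up.
- Item f covers the clinical picture and reads: "Situation at follow-up: chief complaint of symptoms, general condition, vital signs, Quality of Life, HAS-BLED score, etc".
- Item g covers the repeat tests; its opening part reads: "Laboratory and instrumental examination at follow-up: biochemical indicators, electrocardiogram, cardiac color ultrasound, cardiac CTA, craniocerebral CT and MRI".

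Quality of life appears in item f and in no other item. Section 8.1, item 9, asks for international or Chinese versions of the relevant scales, without naming an instrument or a time point. The end point lists in sections 2 and 4.2 do not include quality of life.

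**The concern.** When patients choose their own group, those who accept a more intensive care mode may differ in quality of life from those who decline, before the mode can have had any effect. The entry value of the outcome is the most direct means of dealing with this. It can be used to match controls, and follow-up scores can be compared with adjustment for it.

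The form, as listed, asks for the score only after the groups have diverged. The choice between matching, adjustment and change scores can be left to an analysis plan, but a measurement that was not taken cannot be supplied by one. The data-collection list in the protocol is therefore the right place to settle this. At stake is the interpretation of one exploratory comparison, not the main result of the registry.

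**Working it through.** The plan gives no figure to reproduce. The 1,200 in section 5.3 is a recruitment expectation and does not bear on this point. The check is a comparison of the lists.

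**Step 1: follow-up to entry.** Item f names 5 things (chief complaint, general condition, vital signs, quality of life, HAS-BLED). Item g names 6 (biochemistry, electrocardiogram, cardiac ultrasound, cardiac CTA, craniocerebral CT and MRI counted as one, artery evaluation). The total is 5 + 6 = 11. Three of these have a named counterpart in item b and six in item c, so 9 of 11 are paired. The two unpaired are quality of life and HAS-BLED, and of these only quality of life is named in the comparison objective. Cardiac function, its neighbour in that objective, has cardiac ultrasound in both c and g.

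**Step 2: entry to follow-up.** Item b names 6 things and item c names 9, so 15 in all. Nine are paired. The other 15 − 9 = 6 have no follow-up counterpart: CHA2DS2-VASc, nutrition questionnaire, epidemiological data, nutrient index, dynamic electrocardiogram and foaming test. The list is therefore loose in both directions. The count in step 1 shows that quality of life is not named at entry; it does not show a deliberate rule.

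**Step 3: could another entry item cover it?** General condition in item b is the nearest. Item f lists general condition and quality of life separately, so the protocol treats them as different things.

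**Step 4: what can still be adjusted for.** Age and comorbidity (item a), symptoms, general condition and CHA2DS2-VASc (item b) and cardiac ultrasound (item c) are all named at entry. Matching or adjustment on these is possible. What is missing is the entry value of the outcome itself.

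**Step 5: what the bias depends on.** Suppose a gap of d standard deviations in entry quality of life remains after matching on the other variables, and follow-up scores rise by b per unit of entry score. With no true effect, the expected follow-up difference is b × d. The protocol gives neither b nor d. If, purely as an assumption, b is 0.5 to 0.7 and d is 0 to 0.3 SD, the bias runs from 0 (d = 0) to 0.7 × 0.3 = 0.21 SD. The range starts at zero because nothing in the document excludes a zero gap. It shows the mechanism and is not an estimate for this registry.

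**The case against.** Several points on the other side stand.

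- **The lists are open.** Items a, b, c, f and g all end open-ended, and the actual form is not shown. A reader might infer that quality of life will never be recorded at entry. The document does not support that; it shows only that nothing instructs sites to record it. The requirement in sections 7.2 and 8.2 to leave no item empty does not help if the item is absent.
- **Improvement need not mean change from baseline.** In the objective the word also governs risk of death, which has no baseline value. It may mean only a better result in one group. A reader might infer that a change score is promised and cannot be computed, but the text does not fix that. The confounding problem remains under either meaning.
- **Adjustment is not impossible.** The other entry variables can be used, so it would be too strong to say that the form supports no adjustment.
- **The standing of the comparison is low.** Quality of life is to be explored, is in neither end point list, and section 5.3 makes the comparison itself conditional.
- **False-positive rates.** A reader might want to turn the bias into a chance of a spurious significant result. That would need a group size and an entry gap that the document does not give. The answer would follow from the assumed gap, so no rate is offered here.

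The objections limit the scope and strength of the point. They do not supply an entry score.

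**Conclusion.** The point holds in a limited form. Followed as listed, the form yields quality-of-life scores at follow-up only, in groups formed by patient choice. A follow-up difference could be adjusted for other entry characteristics but not for entry quality of life. It therefore could not be separated from who agreed to the mode. The size and direction of the resulting bias cannot be derived from the document.

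This affects one exploratory objective. The primary composite and the listed secondary end points are untouched, and follow-up values can still be described. The conclusion assumes that the form will follow the named items; if the actual form already takes an entry score, the protocol only needs to say so. The change is worth making because it is cheap now and a missing entry score cannot be recovered once patients have been treated.

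**What to change.** Add quality of life to item b of section 7.1. Name one instrument and use the same one in item f, which at present names none. Record and date the entry score before the patient chooses a group and before any study-related procedure where possible. A score taken after either may already reflect the care mode, and adjusting for it could remove part of the effect. Include the entry score among the matching factors and compare follow-up scores adjusted for it.

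Some patients with new stroke may not be able to answer before these points. The protocol already places their aetiological work-up later: "After the disease stabilized, the examination related to etiological diagnosis should be improved". Flag entry scores obtained late and show these patients separately.

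If no entry score will be collected, limit the quality-of-life objective to a description of follow-up values.

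The cost is a revision of the form and one short questionnaire per patient, at an admission assessment that already includes a nutrition questionnaire. Entry scores in new-stroke patients will be harder to interpret, because they may partly reflect the acute deficit. Even a well-timed score reduces confounding rather than removing it, since the score is measured with error and patients may differ in other ways.
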